9.5 Baseline Assessments

General information will be collected from participants via the clinical record as will information pertaining to their antibiotic usage, their comorbidities, and more specific cystic fibrosis information as per below:

- Age.
- Sex.
- Height
- Weight.
- BMI.
- Smoking status.
- Antibiotic usage (last three months).
 - IV antibiotics.
 - Oral antibiotics.
 - Nebulised antibiotics.
 - Long term antibiotic usage.
- Co-morbidities.
- Cystic Fibrosis specific information.
 - o SNOT-22 score
 - \circ $\;$ FEV1% score. .
- Is the participant undergoing sinus treatment.
- Is the participant used a nasal spray.
- Is the participant recovering from endoscopic surgery.

9.6 Study Visits and Follow Up

During their routine clinic meeting (Visit 1), all participants of the study will provide the

following data/samples:

- SNOT-22 questionnaire.
- Cystic Fibrosis Quality of life (CFQ-R) questionnaire.
- Clinical Record Form (CRF) data.
- Nasal swab.
- Sputum sample.
- Nasal rinse wash solution.

Bwrdd Iechyd Prifysgol Caerdydd a'r Fro Cardiff and Vale University Health Board

Participants will then be given a nasal rinse kit (with/without manuka honey depending on the group they have been assigned), a set of instructions on how to use the kit, and a compliance diary. Participants will use their respective kits as per the instructions daily and fill in the compliance diary, ensuring to make note of any observations in the compliance diary. Participants will then return to the AWACFC 31 days (+/- 7 days) later for their standard follow up appointment (Visit 2). During this visit a second set of data/samples will be collected as per below:

- SNOT-22 questionnaire.
- Cystic Fibrosis Quality of life (CFQ-R) questionnaire.
- Clinical Record Form (CRF) data.
- Nasal swab.
- Sputum sample.
- Nasal rinse wash solution.

9.7 Sample Handling

Samples will be handled in accordance with HTA regulations and the safety operating procedures (SOPs) set out in NHS/university procedures. Participant samples will be processed and destroyed within 7 days according to local HTA regulations (bacterial cells and bacterial DNA extracted from participant samples will be kept as per the respective SOPs. Any material left over after processing will be disposed of via an approved method.

9.8 Discontinuation/Withdrawal of Participants

All participants have the right to withdraw from the study at any time. In addition to this, the chief investigator (CI) may discontinue a participant from the study at any time if the they consider it necessary. The reason for withdrawal will be recorded on the CRF. The participant will be replaced if possible within the time frame using the same recruitment procedure as was used for the original participant. If you wish to withdraw from the study, all identifiable samples will be destroyed, however all the data generated up to the date of your withdrawal will remain for analytical purposes. Withdrawing from the study will in no way affect your current or future care. If in the future, you were no longer able to give consent to partake in the study, we would follow the procedure as if you had withdrawn from the study

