12.3 Analysis of Outcome Measures/Endpoints

All participant data will be analysed by the academic research team after the end point of the study. The data will be sorted into the two treatment groups before analysis is carried out. The

primary outcome measures will be to determine whether the SNOT-22 score of the manuka honey treatment group has improved compared to the standard treatment. The secondary outcomes will be to see if; the lifestyle questionnaire scores have improved, the amount/type(s) of bacteria has changed, and whether the structure/composition of sputum mucus has changed in the same two groups. If any participants withdrew before the second visit/second set of samples were taken then that data will be excluded from analysis.

Bwrdd lechyd Prifysgol Caerdydd a'r Fro Cardiff and Vale University Health Board

13. Data Management

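### Sections 9.8 and 12.3 provide only for leaving the study, so an intolerance exit handled that way loses its after-treatment SNOT-22 and drops out of the primary comparison

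*Combined protocol and SAP*

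**What the plan says.** Section 9.8 of the combined protocol and SAP gives two main ways out. The participant's is "All participants have the right to withdraw from the study at any time". The chief investigator's is that he or she "may discontinue a participant from the study at any time if the they consider it necessary". Both are worded as leaving the study. One recording rule follows them: "The reason for withdrawal will be recorded on the CRF". Then comes replacement: "The participant will be replaced if possible within the time frame using the same recruitment procedure as was used for the original participant". For a participant who chooses to withdraw, "all the data generated up to the date of your withdrawal will remain for analytical purposes". Loss of capacity to consent is handled as a withdrawal.

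Sections 9.1 and 9.6 schedule SNOT-22 at Visit 1 and Visit 2 only, so Visit 2 supplies the sole after-treatment score. Sections 3 and 15.5 describe that visit as part of standard care.

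Section 12.3 defines the primary outcome as "whether the SNOT-22 score of the manuka honey treatment group has improved compared to the standard treatment". On early exits it says: "If any participants withdrew before the second visit/second set of samples were taken then that data will be excluded from analysis".

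**The concern.** The primary question compares two randomised groups. Section 9.4 leaves participants unblinded, and section 10.1 puts 40% honey in one arm's rinse only. Section 11.1 lists nasal irritation among the events to record and expects temporary congestion and ear discomfort with any rinse. Some of these complaints overlap with what SNOT-22 measures. Exits for intolerance may therefore be related to the outcome and may differ by arm.

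If people who tolerate the honey poorly are taken out of the study, the honey scores that remain come more from those who tolerate it. The comparison is then no longer between the groups as randomised. Replacement restores the head count but not the missing scores. New participants go through the same random allocation, so replacement neither creates nor removes the shift. A Visit 2 score that was never collected as study data cannot be recovered at analysis.

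**Working it through.** **Who is affected, from the text**

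- A participant who stops rinsing but does not leave stays on the 9.6 schedule, completes SNOT-22 at Visit 2 and is not excluded by 12.3. Nothing is lost.
- A participant who withdraws before Visit 2 because of intolerance has study data up to the withdrawal date only, that is, the Visit 1 SNOT-22. Section 12.3 excludes that person.
- A participant whom the chief investigator discontinues before Visit 2 has left the study. Section 12.3 speaks only of those who withdrew. Section 9.8 puts both exits under one heading and one reason-for-withdrawal entry, so the exclusion most naturally covers this person too.

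**The plan's own figure**

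Section 12.2 gives SD 14.5, difference 8.9, two-sided, 80% power, and a sample size of at least 21. With alpha 0.05 (assumed, as it is not stated) and 14.5 used as the SD of the change:

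n = (1.960 + 0.842)² × 14.5² / 8.9² = 20.8, rounded up to 21.

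This reproduces the plan, so 14.5 is used below as the SD of change.

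**Illustrative shift**

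The documents give no exit rate, no correlation between exit and change, no allocation ratio and no named between-group test for SNOT-22. All are assumed here. Let p be the proportion exiting in an arm and r the correlation between tolerating the rinse and SNOT-22 improvement. Under a normal model, removing the least tolerant fraction p raises the mean improvement of those who remain by

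r × SD × φ(z_p) / (1 − p).

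The factor φ(z_p)/(1 − p) is 0.350 at p = 20%, 0.195 at 10% and 0.109 at 5%. For r = 0.5, r × SD = 7.25; for r = 0.3 it is 4.35. The between-arm shift is honey minus control, with no true effect:

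| Exits, honey v control | r = 0.5 | r = 0.3 |
|---|---|---|
| 20% v 0% | 2.54 | 1.52 |
| 10% v 0% | 1.41 | 0.85 |
| 20% v 10% | 1.12 | 0.67 |
| equal rates | 0 | 0 |
| 5% v 20% | −1.75 | −1.05 |

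At 15 per arm, 20% is three people. The shift is proportional to the change SD. If the correlation between the before and after scores were 0.7 or 0.3, the change SD would be 14.5 × √(2 × 0.3) = 11.2 or 14.5 × √(2 × 0.7) = 17.2, and the largest entry would be about 2.0 or 3.0.

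**Against the precision of the comparison**

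- 15 v 15: SE = 14.5 × √(2/15) = 5.29
- 12 v 15: SE = 14.5 × √(1/12 + 1/15) = 5.62, so 2.54 is 45% of it
- 12 v 13.5: SE = 14.5 × √(1/12 + 1/13.5) = 5.75, so 1.12 is 19% of it and 0.67 is 12%

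Against the 8.9-point difference, 2.54 is 29% and 0.67 is 7.5%.

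**False-positive rate**

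This was simulated under no effect (30,000 runs, 15 randomised per arm, two-sided t test at 5%). At r = 0.5 without replacement, the total is 7.2% for 20% v 0% (6.4% favouring honey, 0.8% favouring control), 5.6% for 10% v 0%, 5.4% for 20% v 10% and 5.0% for 20% v 20%. With randomly allocated replacement until 30 are analysed, 20% v 0% gives 7.2% and 20% v 10% gives 5.2%. At r = 0.3 without replacement, those two cases give 5.7% and 5.1%. Simulation error near 5% is √(0.05 × 0.95/30,000) = 0.13 percentage points, so 5.1% and 5.2% cannot be told from 5%.

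**A simpler cross-check**

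Suppose 15 per arm, k exits all in the honey arm with zero change, and the rest of that arm improving by 8.9. Dropping the exits overstates the honey mean change by k/15 × 8.9, which is 0.6 for k = 1, 1.8 for k = 3 and 3.0 for k = 5. This is the same order of size.

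**The case against.** The strongest reply is that the text does not send intolerant participants out of the study. The investigator's power in 9.8 is discretionary, and anyone who simply stops rinsing is followed and analysed. That stands. A reader might infer that every intolerance case is lost to the primary analysis, and the documents do not say so. The point covers only cases handled as an exit under 9.8.

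A second reply is that 12.3 does not mention discontinuation by the investigator, and that the data cut-off in 9.8 is addressed to participants who choose to withdraw. That also stands: applying both to investigator discontinuation is inference. The ambiguity is itself worth removing.

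Third, section 11.4 lets investigators take immediate safety measures, which could include pausing the rinse. It covers urgent hazards, however, and says nothing on ordinary intolerance or on keeping the person in follow-up. The study procedures document that section 9 refers to was not available and may contain a rinse-stopping rule. The point is therefore limited to 9.6, 9.8 and 12.3, and 12.3 would need to agree with any such rule.

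Fourth, this is a pilot. With 15 per arm and SD 14.5, power for 8.9 points is Φ(8.9/5.29 − 1.96), about 39%, so a shift under half a standard error may not change how the result is used. That limits the consequence. But section 3 expects the study to inform a larger one, and exits by arm and reason are useful information for that purpose.

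Finally, including rinse-stoppers is a choice of what to estimate. It is, but a comparison of groups as randomised fits the stated primary question better than one restricted to those who stayed.

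**Conclusion.** The gap is real but conditional. As written, 9.8 offers only exits from the study, and 12.3 excludes those who withdrew before the sole after-treatment SNOT-22. Intolerance handled by either route is then absent from the primary comparison, explicitly for participant withdrawal and by natural reading for discontinuation by the investigator.

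Size and direction are unknown. With honey-heavier exits, assumed correlations of 0.3 to 0.5 and a change SD of 14.5, the shift is about 0.7 to 2.5 points, or roughly 12% to 45% of a standard error. It is zero at equal exit rates and favours control if control exits are more frequent. False-positive inflation is modest even in the worst case shown (7.2% against 5%).

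A reader might infer that the plan biases the trial towards honey. The documents do not support that, because they give no exit rates and expect some nasal discomfort with any rinse. This is a cheap improvement.

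**What to change.** **Section 9.8.** State that the chief investigator or the participant may stop the study rinse without leaving the study, and define withdrawal of consent separately. Record the rinse stop date and reason on the CRF. Do not replace people who only stop the rinse. Keep the scheduled Visit 2 SNOT-22 and CFQ-R for everyone except those who withdraw consent or lose capacity, whom 9.8 already treats as withdrawn.

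**Section 12.3.** Analyse everyone with Visit 2 data in their randomised group. Limit exclusion to those with no Visit 2 data, whatever the reason, and report exits by arm and reason.

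**Cost.** A few sentences in two sections, two CRF items and a line in the information sheet, through the amendment route in 9.9. No visit is added, because Visit 2 and its questionnaires are already scheduled. Clinical judgement on when to stop the rinse is unchanged. The downside is that the estimated honey effect will include people who stopped and may be smaller.

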9.9 Study Amendments

The CI will seek approval for any substantial amendments to the protocol or other study documents from the Sponsor (Swansea University), Research Ethics Committee (REC) and NHS Research & Development (R&D) Office(s) where appropriate. Amendments to the protocol or other study documents will not be implemented prior to these approvals being granted. Non-substantial amendments will be notified to the REC for information and may also need to be reviewed and accepted by R&D departments, or through other research governance mechanisms, before they can be implemented in practice. It is the sponsor's responsibility to classify amendments as being non-substantial or substantial and the chief investigator will seek advice from the sponsor when necessary.

9.10 Definition of End of Study

The end of the study will be the date of the last visit of the last participant undergoing the trial.

10. Products, Devices, Techniques, and Tools.

Below is a brief (layman) explanation of some of the devices, techniques and tools being employed in this study. Each element has been expertly selected using good clinical and academic judgement to ensure the primary and secondary objectives can be answered in the most efficient way possible.

10.1 Devices

Medihoney.

Medihoney (a sterile medical grade honey) is manufactured by Integra Lifesciences and is CE marked. The honey will be dissolved into the standard sinus rinse (which forms part of standard clinical care for the treatment of CF sinus infections) at a final concentration of 40 %.

10.2 Techniques and Tools

SNOT-22 Questionnaire.

The SNOT-22 questionnaire is a validated method used to determine the severity of the social/emotional consequences of a patient's nasal disorder. This questionnaire has no right or wrong answers and should reflect the feelings of the patient to their nasal disorder (ranging from "no problem" through to a "moderate problem", with "problem as bad as it can be" having the highest rating). Some of the areas surveyed in this questionnaire relate to; sneezing, runny nose, dizziness, nasal discharge, ability to sleep, fatigue etc...

CFQ-R Questionnaire.

The CFQ-R questionnaire is used to understand the impact of CF and the associated treatments on the patients everyday life, allowing adjustments to be made in treatments to benefit the patient. The CFQ-R is a quality of life questionnaire that has been specifically designed for CF patients. Some of the areas surveyed in this questionnaire relate to; demographics, quality of life, school/work and daily life activities, and symptom difficulties.

CRF.

The CRF is used to record various data pertaining to the patient's demographics, antibiotic usage, comorbidities, and specific information relating to their condition (CF) and their treatment. This form is based on facts rather than the previous two questionnaires which focus more on the patient's feelings.

Microbial Diversity Assessment (Basic Microbiology).

Basic microbiological techniques (culturing bacterial species on selective bacterial growth media) will be used to determine the total number of bacteria in each biological sample. The selective growth media will provide some indication as to the bacterial species present in the samples and the ratio of them.

Microbial Diversity Assessment (Bioinformatics).

Advanced bioinformatics techniques (sequencing of bacterial cells) will be used to determine the community composition and the species of bacteria present within biological samples. This particular method will allow non-culturable bacterial cells to also be identified (which wouldn't be picked up through basic microbiology methods).

Sputum Mucus Structure.

Bruker Tensor high throughput Fourier transform infrared spectrometers will be used to determine the molecular structure of mucus sputum.

11. Safety Reporting

11.1 Adverse Events

An Adverse Event (AE) is any untoward medical occurrence in a trial participant which does not necessarily have a causal relationship with this treatment. An AE can therefore be any unfavourable and/or unintended sign (including abnormal laboratory finding), symptom, or disease. We will therefore record signs of an allergic reaction such as;

- Rashes.
- Hives.
- Itching.
- Red and/or swollen skin.
- Blistered and/or peeling skin
- Wheezing.
- Tightness in the chest or throat.
- Trouble breathing, swallowing, and/or talking
- Unusual hoarseness
- Swelling of the mouth, face, lips, tongue, and/or throat
- Nasal irritation.

The following (see below) may be expected with routine use of a sinus rinse protocol and will therefore be recorded but not reported. May can often be avoided by following the administration instructions in the patient information booklet.

- Temporary increase in nasal congestion (often improves with continued use).
- Ear discomfort whilst rinsing.
- Drainage of leftover solution from the nose after rinsing.
- Accidental ingestion of solution (not recommended but deemed not harmful).

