8.2 Exclusion Criteria

The following criteria will be used to determine the ineligibility of a patient to participate in the study.

- The patient has ever tested positive for the bacteria Mycobacterium tuberculosis.
- The patient is currently using a nasal rinse protocol.
- The patient has undergone sinus surgery within 6 months.
- The patient suffers from nasal bleeding.
- The patient is currently undergoing systemic antibiotic therapy for infective exacerbation.
- The patient is using overnight oxygen via nasal cannula.
- The patient is participating in another clinical trial or has done so within the last 30 days.
- The patient has a known allergy to bee products.
- The patient has an objection to the use of bee products

Bwrdd Iechyd Prifysgol Caerdydd a'r Fro Cardiff and Vale University Health Board

9. Study Procedures

(See attached study procedures document)

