11.2 Serious Adverse Events

A Serious Adverse Event (SAE) is any adverse event that meets one or more of the criteria

listed below:

- Results in death
- Is life-threatening
- Requires hospitalisation or prolongs existing hospitalisation
- Results in persistent or significant disability or incapacity
- Results in a congenital anomaly or birth defect
- Other medically important condition

Bwrdd lechyd Prifysgol Caerdydd a'r Fro Cardiff and Vale University Health Board

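### Section 11.1 defines adverse events broadly but commits to recording only allergic signs and four rinse effects, so non-serious nosebleeds, exacerbations and sinus or ear infections have no stated systematic recording

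*Combined protocol and SAP*

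**What the plan says.** Section 11.1 opens with the definition: "An Adverse Event (AE) is any untoward medical occurrence in a trial participant which does not necessarily have a causal relationship with this treatment". It extends this at once: "An AE can therefore be any unfavourable and/or unintended sign (including abnormal laboratory finding), symptom, or disease". Neither seriousness nor relatedness to the rinse limits the scope.

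The recording commitment comes next: "We will therefore record signs of an allergic reaction such as". Eleven examples follow. Most are skin, airway or swelling signs, and the last is nasal irritation. A second list gives four effects that "may be expected with routine use of a sinus rinse protocol and will therefore be recorded but not reported": a passing rise in congestion, ear discomfort during the rinse, leftover solution draining out, and swallowing some solution by accident.

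Section 8.2 lists among the reasons not to enrol: "The patient suffers from nasal bleeding" and "The patient is currently undergoing systemic antibiotic therapy for infective exacerbation".

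**The concern.** The recording commitment does not follow from the definition. The word that joins them (therefore) suggests that recording allergic signs carries the definition out, but allergic signs are one class within it. The words that introduce the examples make that list open-ended, but open-ended only for signs of allergy. A nosebleed, a chest exacerbation treated without admission, or a new sinus or ear infection meets the definition and is named in neither list.

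These events bear on tolerability. Participants in the honey group put a 40% honey solution into the nose daily for 30 days (sections 5 and 10.1), and section 3 says that the results could inform a more in-depth study. Section 4 sets no safety objective and section 12 no safety analysis, so section 11.1 is the main basis for tolerability data. Participants know their group (section 9.4), so events that surface only when volunteered may be volunteered differently in the two arms. Systematic enquiry in both arms reduces that risk.

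**Working it through.** No arithmetic underlies this point, and the plan states no figure to reproduce. The check sets the definition, the recording commitment and every other visible data-collection route side by side.

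**1. The two lists in section 11.1.** The first has 11 items and the second 4. None names nasal bleeding, infective exacerbation, or sinus or ear infection. The nearest are nasal irritation, wheezing, chest tightness and trouble breathing in the first list, and ear discomfort while rinsing in the second. These are symptoms that may accompany such events but do not identify them.

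**2. The entry criteria in section 8.2.** Nasal bleeding is itself an exclusion. For exacerbation, the exclusion is systemic antibiotic treatment under way at entry. The protocol thus treats both as relevant at screening but names neither for recording during treatment.

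**3. Other routes by which an event could reach the data.**

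| Route | What it could catch | What it leaves open |
|---|---|---|
| Serious adverse events (11.2, 11.3) | Any event meeting a seriousness criterion | Non-serious nosebleeds, exacerbations managed without admission |
| Compliance diary (9.1, 9.6) | Whatever a participant chooses to note | No stated review, classification or transfer to adverse-event data |
| CRF at both visits (9.5, 10.2, 13.2) | Antibiotic courses, comorbidities, CF and treatment details | No adverse-event field described; bleeding would not show in antibiotic data |
| Reason for withdrawal (9.8) | Events that lead someone to leave | Events in those who stay; section 12.3 also excludes from analysis the data of those who withdraw before Visit 2 |

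**4. The antibiotic look-back.** Section 9.5 lists a three-month window under baseline assessments. The documents do not say which window applies at Visit 2. If it is the same one, then with three months taken as about 90 days and Visit 2 at day 31, the window reaches back 90 − 31 = 59 days before Visit 1. Without course dates, it could not separate courses taken before treatment from those taken during it.

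**5. Result.** No visible section commits to recording all events that meet the definition, and no other route is set up to collect the non-serious events outside the two lists.

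**The case against.** The strongest reply is that a loosely worded sentence does not mean that events are lost. The text never says that nothing else will be recorded. Participants are asked to note what they observe in the diary, and a nosebleed is an obvious thing to note. A treated exacerbation may show in the Visit 2 CRF as an antibiotic course, or under wheezing or trouble breathing. Serious events are judged against the full definition rather than the two lists, so one that "Requires hospitalisation or prolongs existing hospitalisation" is caught whatever its type. Section 9 points to a separate study procedures document, which was not available and may contain adverse-event prompts.

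Much of this stands. A reader might infer that nosebleeds and exacerbations will go unrecorded during treatment, or that the named items are all that can be recorded. The documents support neither inference, because each route above may catch some events and the allergic list is illustrative. Nor does section 8.2 exclude exacerbation as such. It excludes current systemic antibiotic therapy for one, and an entry exclusion does not by itself create an on-treatment safety item.

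The reply does not supply the missing commitment. Each route is partial, and none is described as a way of collecting non-serious adverse events consistently in both arms.

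**Conclusion.** The point holds as an inconsistency within section 11.1: the definition is broad, the recording commitment is narrower, and no visible text bridges them. Non-serious nasal bleeding, infective exacerbation and new sinus or ear infection are not named for systematic recording, so the pilot's comparison of tolerability between arms would be incomplete. How many events would be missed cannot be estimated, because the documents give no event rates.

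The conclusion assumes that the study procedures document and the CRF, neither of which could be seen, do not already require full recording. If they do, what remains is a missing cross-reference. It does not show that the study will collect no such events, or that a report would claim that none occurred. This is a cheap improvement and leaves the efficacy design unaffected.

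**What to change.** Reconcile the definition and the recording commitment in section 11.1. State that all adverse events meeting the definition, in both arms, from the first rinse to Visit 2, are recorded on the CRF with date, severity and relatedness. Keep the two existing lists as prompts, and add nasal bleeding, infective exacerbation and sinus or ear infection to them. The rule that the four expected rinse effects are recorded but not reported can stay, since it governs reporting. If the study procedures document already covers this, cross-refer to it in 11.1 instead.

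The cost is a change to the protocol wording, a few CRF lines and a short enquiry at the existing Visit 2, with no extra visit. The downside is that more CF events unrelated to the rinse will have to be recorded. The change concerns data collection only and alters no treatment or clinical rule.
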